7.1. Discontinuation of Study Intervention

Participants unable to manage drug toxicity or tolerate investigational product (either formulations of CAB or RPV), or meet a protocol-defined withdrawal criterion must have IP discontinued. Where the CAB LA + RPV LA marketed product is not locally available, any participant receiving at least one dose of CAB LA and /or RPV LA who discontinue IP / Withdraw will initiate treatment with HAART and enter the LTFU phase for an additional 52 weeks of follow up. The start of the 52-week follow-up period begins the day of the last CAB LA and/or RPV LA dose with the first visit at Month 3. When the CAB+RPV LA marketed product is locally available participants must enter the LTFU Phase if withdrawing for safety related reasons only.

7.1.1. Liver monitoring event – Increased monitoring

A liver monitoring event is an occurrence of predefined liver chemistry changes that triggers increased monitoring of the participant's liver chemistries, but no action is taken with study treatment unless liver chemistry stopping criteria are met.

Liver monitoring event criteria:

- Baseline ALT $\leq 1.5x$ ULN: ALT $\geq 5x$ ULN and $\leq 8x$ ULN and bilirubin $\leq 2x$ ULN without symptoms believed to be related to liver injury or hypersensitivity.
- Baseline ALT >1.5x ULN: ALT \ge 3x baseline and <5x baseline and bilirubin <2x ULN without symptoms believed to be related to liver injury or hypersensitivity

Actions:

- Notify the medical monitor within 24 hours of learning of the abnormality to discuss participant safety.
- Participant can continue study intervention
- Participant must return every 2 weeks for repeat liver chemistries (ALT, AST, alkaline phosphatase, bilirubin) until resolution or stabilisation (ALT <5x ULN on 2 consecutive evaluations)
- If at any time participant meets the liver chemistry stopping criteria, proceed as described above

7.1.2. Asymptomatic Liver Enzyme Elevations

For asymptomatic subjects who have ALT≥3x ULN, following discussions with medical monitor, ALT and other specific lab tests can be repeated in an unscheduled visit. This may include liver panel tests included in study protocol, even though subject did not meet any liver monitoring or liver stopping criteria.

7.1.3. Liver Chemistry Stopping Criteria

Liver chemistry stopping and increased monitoring criteria have been designed to assure participant safety and evaluate liver event etiology (in alignment with the FDA premarketing clinical liver safety guidance).

http://www.fda.gov/downloads/Drugs/GuidanceComplianceRegulatoryInformation/Guid ances/UCM174090.pdf

Discontinuation of study intervention for abnormal liver tests is required when:

• a participant meets one of the conditions outlined in Section 10.3.1

• when in the presence of abnormal liver chemistries not meeting protocol-specified stopping rules, the Investigator believes study intervention discontinuation is in the best interest of the participant.

Liver Safety Required Actions and Follow up Assessments can be found in Section 10.3.

7.1.4. Temporary Discontinuation

Participants may have a temporary interruption to their study intervention when on oral therapy (oral lead or oral bridging) for management of toxicities. Such interruption of study intervention does not require withdrawal from the study. However, consultation with the Medical Monitor is required.

7.1.5. Restart

If participant meets liver chemistry stopping criteria do not restart the participant with study intervention unless:

- ViiV Healthcare Safety and Labelling Committee (VSLC) approval is granted,
- Ethics and/or IRB approval is obtained, if required, and
- Separate consent for treatment restart is signed by the participant.

Refer to Section 10.3.2 for full guidance.

Background

- Restarts should be limited to cases in which there is clear evidence that the underlying cause of the liver event is not related to study drug.
- For long-acting agents, a restart may actually be continuation of therapy rather than a true re-start due to the timeframe between dose administration relative to decision making on allowing a restart.

- If protocol defined stopping criteria for liver chemistry elevations are met (Section 10.3), study drug must be stopped. Subjects who meet liver chemistry stopping criteria should not be retreated with investigational product unless an exemption has been approved by the VSLC. The algorithm for restart is described in Section 10.3.2 and summarised in Figure 8.
- If the restart is approved by the VSLC in writing, the subject must be provided with a clear description of the possible benefits and risks of drug administration, including the possibility of recurrent, more severe liver injury or death.
- Ethics Committee or Institutional Review Board approval of drug restart must be obtained, as required.
- The subject must also provide signed informed consent specifically for the IP restart. Documentation of informed consent must be recorded in the study chart.
- Study drug must be administered at the dose specified by the VSLC.
- Subjects approved by the VSLC for restart of IP must return to the clinic once a week for liver chemistry tests for a minimum of one month and thereafter for as long as clinically indicated and then laboratory monitoring may resume as per protocol. Longer durations of close monitoring may be required for long-acting IP.

Refer to Section 10.3.2 for full guidance.

7.1.6. Virologic Failure

Only plasma HIV-1 RNA values determined by the central laboratory will be used to assess virologic failure. The use of local laboratory services to assess virologic failure is only allowed with prior approval (before to initiating the study) obtained by the study team with agreed guidance.

7.1.7. Definition of Protocol-Defined Confirmed Virologic Failure

For the purposes of clinical management in this study, CVF is defined as:

Rebound as indicated by two consecutive plasma HIV-1 RNA levels ≥200 c/mL.

7.1.8. Managing Virologic Failure

Following study entry, no changes, or intensification of ART will be permitted prior to protocol-defined virologic failure, outside of the planned protocol regimens. Only plasma HIV-1 RNA values determined by the central laboratory will be used to assess virologic failure (except where the use of a local laboratory for study-specific assessments has been reviewed and approved by the sponsor prior to study start). Baseline plasma HIV-1 RNA is the assessment completed on study Day 1. The definition of confirmed virologic failure does not apply to participants in the LTFU Phase. These participants will be followed for the emergence of viral resistance.

Inadequate adherence or maladministration may be a cause for virologic failure and should be explored as a first step in the management of study participants (e.g., at the first indication of inadequate virologic response or rebound). Upon notification that a participant's HIV-1 RNA plasma level qualifies him/her as a suspected virologic failure (SVF), the Investigator should query the participant regarding intercurrent illness, recent immunization, or interruption of oral therapy.

7.1.8.1. HIV-1 RNA Blips

HIV-1 RNA "blips" are not usually associated with subsequent virologic failure (DHHS, 2019). Although the implications of persistent HIV-1 RNA levels between the lower level of detection and <200 c/mL are unclear, the risk of emerging resistance is believed to be relatively low.

Participants with transient increases in HIV-1 RNA ('blips' HIV-1 RNA <200 c/mL) are not considered suspected virologic failures and do not require a change in therapy.

Participants who have a HIV-1 RNA \geq 50 c/mL at the key analysis timepoints (Month 12, End of Study visit) should return for a repeat HIV-1 RNA as soon as possible but no later than 4 weeks after the date of the Month 12, respectively such that the result falls within the same analysis window.

In order to better characterize HIV-1 RNA 'blips,' if there is a known reason / explanation for the blip (e.g., immunization, allergies, concomitant medication, intercurrent illness, etc), the study team should be notified of the reason and case context.

If the Investigator has concerns regarding persistent low-level viremia (HIV-1 RNA \geq 50 c/mL and <200 c/mL), the Medical Monitor should be contacted to discuss participant management. Following discussion with the Medical Monitor, additional viral load testing may be performed between visits to determine the appropriate participant disposition for the next scheduled visit.

7.1.8.2. Suspected Virologic Failure

Upon notification that a participant's HIV-1 RNA plasma level meets the definition of suspected virologic failure (plasma HIV-1 RNA \geq 200c/mL), the Investigator should confirm the definition is met by initiating a repeat of the HIV-1 RNA assessment.

The following guidelines should be followed for scheduling confirmatory HIV-1 RNA testing to avoid false-positive results:

- Confirmatory testing should be scheduled within 2 to 4 weeks following resolution of any intercurrent illness, during which time the participant should receive full dose of all IP.
- Confirmatory testing should be scheduled at least 4 weeks following any immunization, during which time the participant should receive full dose of all IP.

- If therapy is interrupted* due to toxicity management, non-compliance, or other reasons, confirmatory testing should be scheduled 2 to 4 weeks following resumption of full dose of all IP.
- The participant should have received full dose of IP for at least 2 weeks at the time confirmatory plasma HIV-1 RNA testing is done.

*Note: treatment interruption guidelines above may not apply for participants on CAB LA + RPV LA treatment. The study team should be contacted to discuss any treatment interruptions for participants meeting the definition of virologic failure.

In addition, the Investigator should query the participant regarding intercurrent illness, recent immunization, or interruption of therapy.

Sites should contact the Medical Monitor to discuss individual participants, whenever necessary.

7.1.8.3. Confirmed Virologic Failure

Participants with CVF must be discontinued from study treatment. However, participants who have received at least one dose of CAB LA or RPV LA prior to confirming virologic failure will remain in the study on oral HAART in the LTFU Phase.

A plasma sample from the suspected virologic failure visit as well as Day 1 (if baseline HIV-1 RNA level ≥ 200 c/mL) will be sent for genotypic and phenotypic resistance testing and the result made known to the Investigator when available. Baseline proviral genotyping on Day 1 PBMCs and other genotyping techniques may also be attempted for patient study participants with CVF. A plasma sample from the confirmation visit will be obtained for storage. This sample may be used for possible future analyses, e.g., for genotypic and phenotypic analyses etc.

For all participants who meet CVF, baseline and suspected virologic failure plasma samples with HIV-1 RNA level \geq 200 c/mL will be analyzed in an attempt to obtain genotype/phenotype data on as many samples as possible. Plasma samples for storage will also be obtained at unscheduled visits including confirmation of CVF. Participants may continue to receive study drug at the discretion of the Investigator until results of resistance testing are available at which time the participant must be discontinued from the study. Even if genotype/phenotype data cannot be generated, participant must be discontinued from the study intervention.

If a participant is prematurely discontinued from the study intervention, the Investigator must make every effort to perform the Withdrawal Visit evaluations outlined in the Schedule of Activities Table. These data will be recorded as they comprise essential evaluations needed to be done before discharging any participant from the study.

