CAB LA + RPV LA IM Treatment Administration ⁱ			X	X	X	X	X	X	X			

213199

]		Sa						
Procedure	Screening* up to 35d	Day 1	Month 1	Month 2	Month 4	Month 6	Month 8	Month 10 b	Month 12 b	Withdrawal ^m	Safety Follow-up Visit ^w	Long Term Follow-up ⁿ
	Δ. ř	Oral Lead- in	Dose 1 (D1)	Dose 2 (D2)	Dose 3 (D3)	Dose 4 (D4)	Dose 5 (D5)	Dose 6 (D6)	Dose 7 (D7)	/alm		D B
Participant Visit Reminder Contact	х	х	х	х	х	х	х	х				
Participant Contact Detail Confirmation	x	х	х	х	х	х	х	х				
Patient Toolkit ^s		х	х	х	х			X				
Record Visit Length ^j			х	х		х	х					
Contraception Counseling ^u										х		x
HAART dispensation ^v										х		X
Patient Questionnaires ^k			X		X				х			
Selected Patient Interviews ¹		х							х			
CCI												

213199

	Screening ^a up to 35d		Intervention Period (Month)								Safe	
Procedure		Day 1	1 Month 1	Month 2	Month 4	Month 6	Month 8	Month 10	Month 12	Withdrawa1 ^m	ety Follo Visit ^w	- Long Term Follow-up ⁿ
		Oral Lead- in	Dose 1 (D1)	Dose 2 (D2)	Dose 3 (D3)	Dose 4 (D4)	Dose 5 (D5)	Dose 6 (D6)	Dose 7 (D7)		dn-wo	ip"
Preference Question									X			
Review plan to transition to commercial product or alternative ART ^v											Х	

a) A screening visit will be conducted within 35 days of Day 1. However, it is preferred for Day 1 to be conducted as soon as practical after all screening results are available.

- b) Continue this pattern for visits for the remainder of the study if needed, until CAB LA + RPV LA is locally approved and available. For example, Dose 8 will be conducted as per Dose 6, Dose 9 will be conducted as per Dose 7, Dose 10 will be conducted as per Dose 6 and so on. The exception to this pattern is that no questionnaires, study visit length collection, or patient interviews will be conducted after Dose 7 visit. Visit after Month 12 will be considered, 'extension phase.' See Section 6.8.
- c) Physical exams should be conducted as part of normal routine clinical care but data will not be collected in the electronic case report form (eCRF) unless abnormalities are observed. Medical assessments include any decisions the study staff must make for participant management.
- d) AE and SAEs will not be proactively assessed at M 2, M 6 and M 10. However, all AEs and SAEs reported by study participants **must** be recorded in eCRF at all visits and reported within required timelines as per Section 8.5.1.
- e) Measure vital signs after about 5 minutes of rest in a semi-supine position.

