2.	 HIV-1 infected and must be suppressed on a guideline recommended active HAART regimen for at least 6 months prior to Screening. Any prior switch, defined as a change of a single drug or multiple drugs simultaneously, must have occurred due to tolerability/safety, access to medications, or convenience/simplification, and must NOT have been done for virologic failure (on treatment HIV-1 RNA ≥200 c/mL). 			
3.	 Documented evidence of at least two plasma HIV-1 RNA measurements <50 c/mL in the 12 months prior to Screening: at least one < 6 months prior to Screening and one 6-12 months prior to screening; 			
4.	Plasma HIV-1 RNA <50 c/mL at Screening;			
SEX				
	A female participant is eligible to participate if she is not pregnant (as confirmed by a negative urine human chorionic gonadotrophin (hCG) test at screen and at Day 1), not lactating, and at least one of the following conditions applies: -reproductive potential defined as:			
	• Pre-menopausal females with one of the following:			
	Documented tubal ligation			
	• Documented hysteroscopic tubal occlusion procedure with follow-up confirmation of bilateral tubal occlusion			
	• Hysterectomy			
	Documented Bilateral Oophorectomy			
	• Postmenopausal defined as 12 months of spontaneous amenorrhea [in questionable cases a blood sample with simultaneous follicle stimulating hormone (FSH) and estradiol levels consistent with menopause (refer to laboratory reference ranges for confirmatory levels)]. Females on hormone replacement therapy (HRT) and whose menopausal status is in doubt will be required to use one of the highly effective contraception methods if they wish to continue their HRT during the study. Otherwise, they must discontinue HRT to allow confirmation of post-menopausal status prior to study enrolment.			

b. Reproductive potential and agrees to follow one of the options listed in the Modified List of Highly Effective Methods for Avoiding Pregnancy in Females of Reproductive Potential (FRP) (Section 10.7) from 30 days prior to the first dose of study medication, throughout the study, and for at least 30 days after discontinuation of all oral study medications and for at least 52 weeks after discontinuation of CAB LA and RPV LA.

The investigator is responsible for ensuring that participants understand how to properly use these methods of contraception.

INFORMED CONSENT

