5.2. Exclusion Criteria

Deviations from exclusion criteria are not allowed because they can potentially jeopardize the scientific integrity of the study, regulatory acceptability, or participant safety. Therefore, adherence to the criteria as specified in the protocol is essential.

A participant will not be eligible for inclusion in this study if any of the following criteria apply:

HIV-1 RNA

1. Within 6 months prior to Screening, plasma HIV-1 RNA measurement \geq 50 c/mL;

2. During the previous 12 months, any confirmed HIV-1 RNA measurement ≥200 c/mL

Exclusionary medical conditions

- 3. Women who are pregnant, breastfeeding, or plan to become pregnant or breastfeed during the study.
- 4. Any evidence of a current Center for Disease Control and Prevention (CDC) Stage 3 disease [CDC, 2014], except cutaneous Kaposi's sarcoma not requiring systemic therapy, and historical or current CD4+ counts <200 cells/mm3are not exclusionary.
- 5. Any pre-existing physical or mental condition (including substance use disorder) which, in the opinion of the Investigator, may interfere with the participant's ability to comply with the dosing schedule and/or protocol evaluations or which may compromise the safety of the participant.
- 6. Participants determined by the Investigator to have a high risk of seizures, including participants with an unstable or poorly controlled seizure disorder. A participant with a prior history of seizure may be considered for enrolment if the Investigator believes the risk of seizure recurrence is low.
- 7. Participants who, in the investigator's judgment, pose a significant suicide risk. Participant's recent history of suicidal behavior and/or suicidal ideation should be considered when evaluating for suicide risk
- 8. The participant has a tattoo, gluteal implant/ enhancements or other dermatological condition overlying the gluteus region which may interfere with interpretation of injection site reactions
- Evidence of Hepatitis B virus (HBV) infection based on the results of testing for Hepatitis B surface antigen (HBsAg), Hepatitis B core antibody (anti-HBc), Hepatitis B surface antibody (anti-HBs) and HBV DNA as follows:
 - a. Participants positive for HBsAg are excluded;

b. Participants negative for anti-HBs but positive for anti-HBc (negative HBsAg status) and positive for HBV DNA are excluded

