- 16. Ongoing malignancy other than cutaneous Kaposi's sarcoma, basal cell carcinoma, or resected, non-invasive cutaneous squamous cell carcinoma, or cervical intraepithelial neoplasia; other localized malignancies require agreement between the Investigator and the Study medical monitor for inclusion of the participant prior to inclusion
- 17. Any condition which, in the opinion of the Investigator, may interfere with the absorption, distribution, metabolism or excretion of the study drugs or render the participant unable to receive study medication

- 18. History or presence of allergy or intolerance to the study drugs or their components or drugs of their class.
- 19. Current or anticipated need for chronic anti-coagulation with the exception of the use of low dose acetylsalicylic acid (≤325 mg per day) or hereditary coagulation and platelet disorders such as haemophilia or Von Willebrand Disease.

Exclusionary Laboratory Values or Clinical Assessments (a single repeat to determine eligibility is allowed)

- 20. Any evidence of primary resistance based on the presence of any major known INI or NNRTI resistance-associated mutation, except for K103N, (International AIDS Society [IAS, 2015]) by any historical resistance test result (Wensing, 2019)
- 21. Alanine aminotransferase (ALT) ≥ 5x the upper limit of normal (ULN) or ALT≥
 3x ULN and bilirubin ≥ 1.5 x ULN (with > 35% direct bilirubin)
- 22. Any verified Grade 4 laboratory abnormality. A single repeat test is allowed during the Screening phase to verify a result
- Participant has estimated creatinine clearance <50 mL/min/1.73m2 via the Chronic Kidney Disease Epidemiology Collaboration (CKD-EPI) equation (Levey, 2009).

Concomitant Medications

- 24. Exposure to an experimental drug or experimental vaccine within either 28 days, 5 half-lives of the test agent, or twice the duration of the biological effect of the test agent, whichever is longer, prior to Day 1 of this study;
- 25. Treatment with any of the following agents within 28 days of Day 1:
 - radiation therapy;
 - cytotoxic chemotherapeutic agents;
 - tuberculosis therapy except for isoniazid (isonicotinylhydrazid [INH]);
 - anti-coagulation agents;
 - Immunomodulators that alter immune responses such as chronic systemic corticosteroids, interleukins, or interferons. Note: Participants using short-term (e.g. ≤21 days) systemic corticosteroid treatment; topical, inhaled and intranasal corticosteroids are eligible for enrolment.

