
 Draft listing; may be modified in case of additional substantive data availability. Based on the IAS-USA list of mutations associated with resistance to Bictegravir, Cabotegravir, Dolutegravir, Elvitegravir, or Raltegravir (IAS-USA 2019 resistance mutations update volume 27 issue 3, 2019): T66A/I/K, L74M, E92Q/G, T97A, G118R, F121Y, E138A/K/T, G140A/C/R/S, Y143C/H/R, S147G, Q148H/K/R, S153F/Y, N155H, R263K) and observed mutations during in vitro passage of DTG or seen in a previous DTG study in INI-experienced subjects (study ING112574): H51Y, L74I, L68V/I, E92V, Q95K, E138D, Y143K/S/G/A, P145S, Q146P, V151I/L/A, N155S/T, E157Q, G163R/K, G193E, S230R. Major USA-IAS mutations associated with resistance to INSTI are bolded. Major resistance mutations to other classes (i.e., NRTI, NNRTI, PI) as defined by the International Antiviral Society-USA (IAS-USA). The most up to date IAS-USA guidelines available at the time of DBF will be used in the analysis [Wensing, 2019]. 	
Class	Mutations
NRTIs	M41L, A62V, K65R/E/N, D67N, 69 insert, K70E/R, L74V, V75I, F77L, Y115F, F116Y, Q151M, M184V/I, L210W, T215Y/F, K219Q/E
NNRTIs	L100I, K101E/P, K103N/S, V106A/M, V108I, E138/A/G/K/Q/R, V179L, Y181C/I/V, Y188C/L/H, G190S/A, H221Y, P225H, F227C, M230I/L

Genotype	
PIs	D30N, V32I, M46I/L, I47A/V, G48V, I50V/L, I54V/M/L, Q58E, T74P, L76V, V82A/T/F/L/S, N83D, I84V, N88S, L90M

 Draft listing; may be modified in case of additional substantive data availability. 	

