13.12.5. Efficacy Tables

Efficacy: Tables					
No.	Population	GSK Standard/ Example Shell	Title	Programming Notes	Deliverable
Snapshot					
2.1.	Safety	EFF T1	Summary of Study Outcomes (50 c/mL cutoff) at Month 12 (Intervention Phase) –Snapshot Analysis		HL, M12
2.2.	Safety	EFF T2	Summary of Study Outcomes (50 c/mL cutoff) at Month 12 (Intervention Phase) –Snapshot Analysis Considering Covid-19 Based Events	With expanded COVID-19 related/Non-related categories	HL, M12
2.3.	Safety	SNAPSHOT4	Proportion of Subjects with Plasma HIV-1 RNA \geq 50 c/mL Over Time (Intervention Phase) –Snapshot Analysis	Use Exact (Clopper-Pearson) method for 95% confidence Intervals. Expand to all visits, drop 'n' row, replace x (%) column data with x/n (%), drop '(Intervention Phase)' and use Observed Case instead of Snapshot for EOS	M12, EOS
2.4.	Safety	SNAPSHOT4	Proportion of Subjects with Plasma HIV-1 RNA < 50 c/mL Over Time (Intervention Phase) –Snapshot Analysis	Use Exact (Clopper-Pearson) method for 95% confidence Intervals. Expand to all visits, drop 'n' row, replace x (%) column data with x/n (%), drop '(Intervention Phase)' and use Observed Case instead of Snapshot for EOS	M12, EOS
2.5.	Safety	SNAPSHOT4	Proportion of Subjects with Plasma HIV-1 RNA \geq 50 c/mL Over Time by Subgroup (Intervention Phase) –Snapshot Analysis	Include the following subgroups: country, implementation arm, sex, age group, race group, and CD4 group as mentioned in Section 5.4.2.	M12

Efficacy: Tables					
No.	Population	GSK Standard/ Example Shell	Title	Programming Notes	Deliverable
2.6.	Safety	SNAPSHOT4	Proportion of Subjects with Plasma HIV-1 RNA < 50 c/mL Over Time by Subgroup (Intervention Phase) –Snapshot Analysis	Include the following subgroups: country, implementation arm, sex, age group, race group, and CD4 group as mentioned in Section 5.4.2.	M12
CVF					
2.7.	Safety	VF1	Cumulative Proportion of Subjects Meeting Confirmed Virologic Failure Criteria Over Time (Intervention Phase)		HL, M12
2.8.	Safety	VF2	Proportion of Subjects Meeting Confirmed Virologic Failure Criteria Over Time		M12, EOS
Genotype & Phenotype					
2.9.	Safety	201584/primary_17/T7.1	Summary of the Prevalence of Treatment-Emergent Major Resistance Mutations of INI, NRTI, NNRTI and PI Class at time of CVF - Plasma Sample	Known resistance mutations per Section 13.5.5. Include 95% confidence Intervals using Exact (Clopper-Pearson) method.	HL, M12, EOS

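### The treatment-emergent resistance endpoint has no assured baseline genotype, and the SAP gives no rule for separating emergent from pre-existing mutations

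*Protocol*

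**What the plan says.** A secondary endpoint (Protocol section 3 and 9.4.2; SAP 7.1.1 and 7.1.4.1) is the incidence of treatment-emergent genotypic and phenotypic resistance to CAB and RPV in participants with CVF, with exact 95% confidence intervals.

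**Baseline testing.** Under Protocol 7.1.8.3, plasma from the suspected-failure visit is tested, and plasma from "Day 1 (if baseline HIV-1 RNA level ≥ 200 c/mL) will be sent for genotypic and phenotypic resistance testing". The next paragraph of that section repeats the same 200 c/mL condition for baseline samples. The section also says: "Baseline proviral genotyping on Day 1 PBMCs and other genotyping techniques may also be attempted" in participants with CVF. The Schedule of Activities collects Day 1 PBMCs from everyone. Section 8.10.1 commits only to testing samples from the time of suspected failure.

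**Entry.** Inclusion criterion 4 requires "Plasma HIV-1 RNA <50 c/mL at Screening". Exclusion criterion 1 begins "Within 6 months prior to Screening, plasma HIV-1 RNA measurement" and sets the limit at 50 c/mL or more. Exclusion criterion 20 rules out the "presence of any major known INI or NNRTI resistance-associated mutation, except for K103N", judged on any historical resistance test result.

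**Analysis.** SAP 13.5.5 treats a mutation as present when the residue differs from the wild-type comparator gene. Its major NNRTI list starts "L100I, K101E/P, K103N/S, V106A/M". Table 2.9 is titled "Summary of the Prevalence of Treatment-Emergent Major Resistance Mutations of INI, NRTI, NNRTI and PI Class at time of CVF - Plasma Sample", and its programming note points to the 13.5.5 lists.

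**The concern.** A mutation is treatment-emergent only if it was absent before treatment, so the endpoint needs a pre-treatment comparator for each participant who fails. This population is virologically suppressed on entry, and the one baseline test that the plan commits to depends on viraemia at Day 1. The remaining source is left to discretion, and the SAP does not say how a baseline result, or the lack of one, enters the classification.

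At stake is whether the trial can tell selection by CAB + RPV from mutations already archived when the participant enrolled. CVF cases are likely to be few, so each one carries much of the reported incidence.

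**Working it through.** The plan states no figure for this endpoint, so there is none to reproduce. The check sets the rules side by side and then gives a sense of scale.

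1. **Who has a Day 1 plasma result?** Entry requires below 50 c/mL at Screening and no value of 50 c/mL or more in the preceding 6 months. On timing, the Schedule of Activities states: "A screening visit will be conducted within 35 days of Day 1". A participant must therefore go from below 50 to at least 200 c/mL within at most 35 days for Day 1 plasma to be tested. That is possible but should be rare. The documents give no frequency.

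2. **Who has another baseline result?** Day 1 PBMCs exist for every participant, but their genotyping is permitted rather than required. The proviral route supplies a genotype only. Outside the 200 c/mL condition no baseline phenotype is planned, although the endpoint is also phenotypic. Stored Day 1 plasma exists too, but 7.1.8.3 commits to analysing baseline plasma only at 200 c/mL or more.

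3. **Does entry screening fill the gap?** Only in part. Criterion 20 acts on historical tests but does not require that one exists, and it admits K103N. Protocol 8.1 names demography and prior ART history as screening background and does not mention historical genotypes.

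4. **What does the SAP do with a mutation at failure?** Two readings are open:
   - Apply the 13.5.5 wild-type definition and lists, as the Table 2.9 note directs. K103N present at entry then meets the definition of a major NNRTI mutation at failure, and nothing written removes it from a table headed treatment-emergent.
   - Apply SAP 5.2, under which a missing baseline means that nothing is derived. Emergence is then undefined for each CVF case without a Day 1 genotype.

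5. **Scale.** The documents give no CVF rate. Assume 1% to 3%, applied to the 450 evaluable or 474 enrolled participants in Protocol 9.2:
   - 0.01 × 450 = 4.5 and 0.01 × 474 = 4.7
   - 0.03 × 450 = 13.5 and 0.03 × 474 = 14.2

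   This is about 4 to 14 cases. With n cases, one misclassification shifts the incidence among CVF cases by 1/n. The Clopper-Pearson intervals show how little precision there is in any event:

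| CVF cases (n) | Shift from one case (1/n) | 95% CI for 1 of n |
|---|---|---|
| 4 | 25 points | 1% to 81% |
| 9 (2% of 450) | 11 points | 0% to 48% |
| 14 | 7 points | 0% to 34% |

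**The case against.** The strongest reply has five parts.

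- **Nothing says that pre-existing mutations are counted as emergent.** A reader might infer that they will be. The documents do not support that: no section classifies a mutation that lacks a baseline result, and SAP 5.2 points towards no derivation. The model for Table 2.9 is a program from study 201584, not available here, which may already filter on baseline. This stands, and the conclusion is limited to what could happen.
- **Baseline material does exist.** A reader might infer that the trial has none. That is also wrong: Day 1 PBMCs are scheduled for everyone, 7.1.8.3 foresees genotyping them after CVF, and SAP 13.2.1 would slot a Day 1 result to Screening. What is missing is a commitment to run the assay and a rule for using the result.
- **Subject-level data are reported.** SAP 10.1 and Tables 2.10 and 2.11 present genotypic and phenotypic data for CVF and non-CVF participants, so readers could compare a Day 1 genotype with the failure genotype where one was obtained. This reduces the harm but does not supply a genotype that was never run.
- **K103N was admitted on purpose.** The endpoint concerns resistance to CAB and RPV, and the SAP list is marked as a draft. Both are true. But Table 2.9 counts major mutations across four classes from that list and has no exception for a mutation permitted at entry.
- **This is a descriptive secondary endpoint in an implementation trial.** That limits the severity; the primary analysis is unaffected.

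**Conclusion.** The concern holds in a limited form. As written, a named secondary endpoint has no assured baseline comparator. A Day 1 plasma result should be rare, the proviral result is optional and genotype-only, and the SAP has no baseline rule for treatment-emergent. The outcome is then either possible misclassification, most plainly for K103N, or an endpoint that cannot be derived. The documents do not settle which.

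The size depends on an assumed CVF rate. At 1% to 3%, with about 4 to 14 cases, one misclassified case is worth about 25 to 7 percentage points of the incidence among CVF cases. The documents allow no estimate of how often misclassification would occur. The structural gap does not depend on the assumed rate, and fewer cases make each classification matter more.

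**What to change.** - **Protocol 7.1.8.3 and 8.10.1:** require proviral genotyping of the Day 1 PBMC sample for every participant with CVF. The 200 c/mL condition for plasma can stay.
- **SAP 13.5.5:** define a mutation as treatment-emergent when it is present at suspected or confirmed failure and absent both from the Day 1 genotype (proviral or plasma) and from any available historical genotype.
- **SAP Table 2.9:** add separate rows for mutations present at baseline, including K103N, and for mutations present at failure with baseline unavailable. State the sample source.
- **Phenotype:** label results as at failure wherever no baseline phenotype exists. Proviral genotyping does not close this part of the gap.

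The cost is about 4 to 14 assays under the assumed rate, on samples already collected, plus one SAP definition and two table rows. No visit, dose or stopping rule changes. Proviral assays can fail or detect defective archived virus; the unavailable row and the stated sample source make both visible.
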